1.2 Study Schema

1.3 Schedule of Activities

Procedures	Visit																			
	Enrollment/Baseline visit	Oral Food Challenge	Study Visit 1	Initial dose escalation	Study Visit 2 Visit 1 +1-4 weeks	Dose escalation visit 1	SV 3 Visit 2 +2 weeks	Dose Escalation Visit 2	SV 4 Visit 2 +4 weeks	Dose escalation visit 3	SV 5 Visit 2 +6 weeks	Dose escalation visit 4	SV 6 Visit 2 +8 weeks	Dose escalation visit 5	SV 7 Visit 2 +10 weeks	Dose escalation visit 6	SV 8 Visit 2 +12 weeks	Dose escalation visit 7	SV 9 Visit 2 +14 weeks	Oral Food Challenge
Informed Consent	X																			
Demographics	X																			
Vitals	X	X	X	X	X	X	X	X	X	X	X	X	X	X	X	X	X	X	X	
Spirometry*	X		X	X	X	X	X	X	X	X	X	X	X	X	X	X	X	X	X	
Blood Draw				X															X	
Skin prick test				X															X	
Oral food challenge		X																	X	
Urine Pregnancy	X																		X	
Study Drug Administration			X	X	X	X	X	X	X	X	X	X	X	X	X	X	X	X		
Study Drug Compliance					X	X	X	X	X	X	X	X	X	X	X	X	X	X	X	
AE Review			X	X	X	X	X	X	X	X	X	X	X	X	X	X	X	X	X	
Conmed Assessment	X	X	X	X	X	X	X	X	X	X	X	X	X	X	X	X	X	X	X	

FAQL Questionnaire	X										X
-----------------------	---	--	--	--	--	--	--	--	--	--	---

All dose escalation visits have a window of +/- 2 day

All follow up visits have a window of +/- 7 days

The enrollment/baseline visit, initial oral food challenge (SV 1), will take place at the Pediatric Allergy Clinic at the Cleveland Clinic main campus.

The initial escalation day, dose escalation visits, and final oral food challenge (SV 2-10) will take place in the Clinical Research Unit.

* Spirometry will be performed on all patients ages 5+ and/or at the physician's discretion at the initial study visit as well as the exit oral food challenge. Rather than full spirometry, peak flow will be performed at every updosing visit on all patients ages 4+ and/or if the physician feels that it is developmentally appropriate

2. Introduction

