5.4 Screen Failures

Screen failures are defined as participants who consent to participate in the clinical trial but are not subsequently randomly assigned to the study intervention or entered in the study. A minimal set of screen failure information is required to ensure transparent reporting of screen failure participants, to meet the Consolidated Standards of Reporting Trials (CONSORT) publishing requirements and to respond to queries from regulatory authorities. Minimal information includes demography, screen failure details, eligibility criteria, and any serious adverse event (SAE).

Individuals who do not meet the criteria for participation in this trial (screen failure) because there are no objective signs of an IgE mediated reaction during initial food challenge may not be rescreened. These individuals are not peanut allergic and thus not candidates for the treatment of peanut allergy.

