+105 minutes	4000mg	Examination of skin and auscultation of lungs prior to dose Full physical examination of ears, oropharynx and nose, lungs, and skin after completion of final dose.

*Vital signs including heart rate, blood pressure, respiratory rate and oxygen saturation level to be obtained with any change in physical exam or clinical status

If objective signs of an allergic reaction occur, then the challenge will be stopped, and the subject treated based on the presenting symptoms and clinical judgment of the supervising investigator (Table 4). If no objective signs occur within 2 hours after the last dose is consumed, then the child will be considered not peanut allergic and will not qualify for the study.

Table 4: Oral food challenge stopping criteria

A positive food challenge will be defined by the presence of either of the following:
 
 • One or more major criteria • Two or more minor criteria 
An indeterminate food challenge will be defined by the presence of one minor criterion.
 
A negative food challenge will be defined by the absence of major or minor criteria.
 
All symptoms should be of new onset and not due to ongoing disease. Symptoms must occur no later than 2 hours after the last dose.

Major Criteria

 • Confluent erythematous pruritic rash • Respiratory signs (at least one of the following): 
 Wheezing Inability to speak Stridor Dysphonia Aphonia • $>/= 3$ noncontact urticarial lesions lasting for more than 3 minutes • $>/= 1$ site of angioedema • Hypotension for age not associated with vasovagal episode • Evidence of severe abdominal pain (such as abnormal stillness or doubling over) that persists for more than 3 minutes
Minor Criteria

 • Vomiting (persistent symptoms would elevate to major criterion) • Diarrhea • Persistent rubbing of nose or eyes that lasts for $>/= 3$ minutes • Persistent rhinorrhea that lasts for $>/= 3$ minutes • Persistent scratching that lasts for $>/= 3$ minutes

The subjects with objective signs of an IgE mediated reaction to peanut using standard criteria (Table 4) will be eligible for enrollment.

If patient is found to be study eligible, then a urine pregnancy test will be done on females who have reached the age of child birthing potential.

Initial Dose Escalation

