6.3.2 Assessment of Secondary Efficacy Endpoints

Highest tolerated dose and cumulative dose. The highest dose of roasted peanut protein tolerated by the subject, cumulative total dose of roasted peanut protein tolerated by the subject, and the changes in highest tolerated dose and cumulative tolerated dose from initial OFC to the peanut protein arm of the exit DBPCFC will be analyzed as ordinal variables because of the interval nature of the dosing schedule (Chinchilli et al., 2005). The dose schedule for initial OFC and exit DBPCFC is shown below.

Peanut protein challenge dose schedule at initial (SV 1) and exit (SV 10) oral food challenges.

Oral food challenge	Highest tolerated dose of peanut protein (mg)	Cumulative tolerated dose of peanut protein (mg) at initial OFC	Cumulative tolerated dose of peanut protein (mg) at exit DBPCFC
Initial only	5	5	
Initial only	10	15	
Initial and Exit	25	40	25
Initial only	50	90	
Initial and Exit	100	190	125
Exit only	200		325
Exit only	300		625
Initial only	500	690	
Exit only	600		1225
Initial and Exit	1000	1690	2225
Initial only	4000	5690	

Serum markers of sensitization and tolerance to peanut. Changes in serum markers of sensitization and tolerance to peanut from initial dose escalation visit to final study visit will be analyzed as continuous variables.

Food Allergy Quality of Life Questionnaires (FAQQLQ). The Food Allergy Quality of Life Questionnaire – Parent Form (FAQQLQ-PF) will be used for patients aged 0-12 years (DunnGalvin et al., 2008). The Food Allergy Quality of Life Questionnaire –Teenager Form (FAQQLQ-TF) will be used for patients aged 13-17 year (Flokstra-de Blok et al., 2008). For all FAQQLQ surveys, all questions are scored on an ordered scale from 1 (“no impairment”) to 7 (“maximal impairment”) for calculations. Subscale and summary scores are calculated as item mean scores, on the same scale from 1 to 7. Subscale and summary scores, and changes in subscale and summary scores from enrollment/baseline visit to final study visit, will be analyzed as continuous variables. The MID (minimally important difference) for the FAQQLQ is 0.5 (DunnGalvin et al., 2010), and the change in total score will be dichotomized as greater than or equal to 0.5 or less than 0.5 and analyzed as a binary variable. Scoring of the FAQQLQ is detailed in section 9.3.2.

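### Protocol 6.1.2, read in order, puts the baseline pregnancy test after the entry peanut challenge, whereas the Schedule of Activities puts it before

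*Protocol*

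**What the plan says.** Protocol 5.2 excludes pregnant and lactating participants. Two parts of the protocol then time the first urine test.

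- **Schedule of Activities** (protocol 1.3, copied in SAP 6.3). The row "Urine Pregnancy" has its first mark under Enrollment/Baseline, the column that also holds informed consent. The entry challenge is marked one column later, at SV1. The only other pregnancy mark is at the exit challenge.
- **Protocol 6.1.2, Oral Food Challenge.** The text runs from consent to the dosing steps (Table 3), the stopping criteria (Table 4) and the consequence of the result: "The subjects with objective signs of an IgE mediated reaction to peanut using standard criteria (Table 4) will be eligible for enrollment". The next sentence is "If patient is found to be study eligible, then a urine pregnancy test will be done on females", limited to those old enough to conceive. The Initial Dose Escalation text (SV2) follows.

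Two further statements make study eligibility depend on the challenge result. In 6.1.2, if no objective signs appear, "then the child will be considered not peanut allergic and will not qualify for the study". Section 5.4 bars from rescreening individuals who "do not meet the criteria for participation in this trial (screen failure) because there are no objective signs of an IgE mediated reaction" at the initial challenge.

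**The concern.** The entry challenge raises the peanut dose until objective signs of allergy appear. The signs in Table 4 include wheezing, stridor and hypotension. Protocol 2.3.1 reports that 9 of 63 subjects (14%) in an earlier peanut immunotherapy trial received epinephrine at the screening challenge. A pregnancy exclusion should be checked before such a procedure.

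Staff who follow the Schedule would do that. Staff who follow 6.1.2 in the order printed could challenge a participant with an unrecognised pregnancy and test her only afterwards. The condition in 6.1.2 is also circular: because pregnancy is an exclusion, eligibility cannot be settled before the test is done.

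**Working it through.** The documents state no figure on this point, so the main check is to compare the order of events.

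| Source | Order |
|---|---|
| Schedule (protocol 1.3, SAP 6.3) | Enrollment/Baseline with urine test → SV1 challenge → SV2 |
| Protocol 6.1.2, read in order | SV1 challenge → found eligible → urine test → SV2 |

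The two orders differ, and no statement gives one section precedence. The exit test, by contrast, is placed plainly: the Follow Up text of 6.1.2 has it repeated before the exit challenge. The entry test has no such wording.

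**Peanut protein taken before the test, in-order reading.** Table 3 gives steps of 5, 10, 25, 50, 100, 500, 1000 and 4000 mg. The running sums are 5, 15, 40, 90, 190, 690, 1690 and 5690 mg, which match the SAP 6.3.2 column "Cumulative tolerated dose of peanut protein (mg) at initial OFC". A child who reacts to the first dose has taken 5 mg. A child who reacts only after the last has taken 5690 mg. That is a ceiling, because "If objective signs of an allergic reaction occur, then the challenge will be stopped".

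**Participants who would need the test.** The documents give no age or sex distribution. Assume whole-year ages spread evenly over 1–16, 40–60% girls, and childbearing potential from age 13, 12 or 11 (4, 5 or 6 of the 16 ages). Number = 10 × share of girls × share of ages.

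- Low: 10 × 0.4 × 4/16 = 1.0
- Central: 10 × 0.5 × 5/16 = 1.56
- High: 10 × 0.6 × 6/16 = 2.25

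**Extra tests if testing precedes the challenge.** Some tested girls would then have a negative challenge. Let f be the share of challenged children with no objective signs, assumed to be 10–30% because the documents give no rate. To enrol 10, the expected number of challenge-negative children is 10f/(1 − f).

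- Low (f = 0.1): 1.11 × 0.10 = 0.11
- Central (f = 0.2): 2.5 × 0.156 = 0.39
- High (f = 0.3): 4.29 × 0.225 = 0.96

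This is relative to the in-order reading of 6.1.2. Relative to the Schedule, which already tests before the challenge, it is zero.

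**Age of the result at later steps.** Protocol 8.2 allows screening up to 1 month before the challenge, and SV2 falls 1–4 weeks after SV1. A test at Enrollment/Baseline could therefore be about 4 weeks old at the challenge and about 4 + 4 = 8 weeks old at the first study-drug dose. A test on the day of SV1 would be 1–4 weeks old at that dose.

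**The case against.** The best answer is that the documents largely settle the timing. The Schedule is what staff use visit by visit; it puts the test before SV1, and the SAP repeats it. Section 8.2 has screening confirm that no exclusion applies. The word eligible is also used before the challenge: the opening of the Oral Food Challenge text sends eligible subjects to it, and the synopsis uses the word for patients referred for evaluation. Section 5.5 has the child enrolled at consent. Nor is 6.1.2 strictly chronological: it mentions demographics after the challenge, although the Schedule collects them at Enrollment/Baseline. The change log enters the urine test for 1.3 and 6.1 together, which suggests one test was meant, though it does not say when.

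Much of this stands. It makes the screening reading of eligible possible and shows that the probable intent was to test first. It does not remove the conflict. The sentence immediately before the test ties eligibility to the challenge result, and even on the screening reading nothing in 6.1.2 requires a result before the first challenge dose.

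The objection also has force on the remedy. Simply deleting the post-challenge sentence and relying on Enrollment/Baseline could leave an old result at both the challenge and the first study-drug dose.

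**Conclusion.** This is a minor internal inconsistency in current text, limited to safety. The in-order reading of 6.1.2 is the more natural one but not the only one, so confidence is medium.

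A reader might infer that the plan has no pregnancy check before the entry challenge, or that it means to challenge participants before excluding pregnancy. The documents do not support either: the Schedule has the test on the right side of the challenge, and a known pregnancy is caught at screening under 8.2. A reader might also suspect an effect on the trial's results, but no endpoint, analysis or power figure depends on this.

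The size is small. On the stated assumptions about age, sex and childbearing potential, about 1.0 to 2.3 of the 10 enrolled would need the test, and the number with an unrecognised pregnancy is likely to be none. The case for correcting it is that it concerns a safety exclusion in children and costs almost nothing.

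**What to change.** In protocol 6.1.2, move the pregnancy-test sentence from after Table 4 to before Table 3, and word it as plainly as the exit test, for example: *Females of childbearing potential must have a negative urine pregnancy test before the first SV1 challenge dose.* Do the test at Enrollment/Baseline, as the Schedule has it, or on the day of SV1 if Enrollment/Baseline falls on an earlier date. The Schedule mark can stay; a footnote could record the SV1-day option.

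The cost is one sentence moved and reworded. No visit is added, since "The enrollment/baseline visit, initial oral food challenge (SV 1), will take place at the Pediatric Allergy Clinic" and the test can be done at either. There are two downsides. A girl who then fails screening at the challenge will occasionally have been tested: about 0.1 to 1.0 extra tests in the whole study against the in-order reading, and none against the Schedule. And the result will be 1–4 weeks old at the first study-drug dose, or up to about 8 weeks if the test is done only at an early Enrollment/Baseline visit. The change does not rule out a repeat test at SV2, should the sponsor want one.

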5.2 Exclusion Criteria

Exclusion Criteria
History of life threatening peanut anaphylaxis
Asthma requiring more than medium dose ICS
Prior participation in OIT, SLIT or EPIT
Oat allergy
Cardiovascular Disease
Use of beta-blockers (oral), angiotensin converting enzyme inhibitors, angiotensin receptor blockers, or calcium channel blockers
Use of steroid medications in the following manners:
Daily oral steroid dosing for greater than 1 month during the past year OR
Burst or steroid course in the past 3 month before inclusion OR
Greater than 2 bursts oral steroid courses in the past year of at least 1 week duration
Pregnancy or lactation
Eosinophilic Gastrointestinal Disease
History of food protein-induced enterocolitis (FPIES)
History of developmental delay or speech delay that precludes age-appropriate communication, in the opinion of the investigator

Abbreviations: ICS, inhaled corticosteroid, OIT, oral immunotherapy, SLIT, sublingual immunotherapy, EPIT, epicutaneous immunotherapy

A history of life-threatening anaphylaxis is defined as a reaction involving respiratory failure, hypotension or neurologic compromise. Medium dose ICS is defined by the National Heart, Lung, and Blood Institute asthma guidelines. Patients with oat allergy, while rare, are to be excluded as this will serve as the placebo for our exit food challenge (SV10).

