6.1.2 Dosing and Administration

Oral Food Challenge

After informed consent is obtained (and assent when relevant), eligible subjects will undergo an open roasted peanut graded food challenge to 4000 mg of peanut protein to confirm peanut allergy and to determine the amount of peanut protein required to induce an allergic reaction at baseline. An oral food challenge is the gold standard for diagnosis of food allergy. PB2 peanut powder (PB2 Foods, Tifton, GA) will be used exclusively for this challenge, mixed in a vehicle of the family's choice (such as applesauce, pudding, etc.).

Subjects will be instructed to hold medications with strong antihistamine properties for five days prior to the challenge (diphenhydramine, loratadine, desloratadine, cetirizine, levocetirizine, fexofenadine, azelastine). The challenge will not be performed in the setting of acute illness, including febrile illness, asthma exacerbations, and significant flares of atopic dermatitis.

The oral food challenge protocol is outlined in Table 3. The initial oral food challenge will take place under the supervision of a trained Allergy/Immunology investigator and trained Allergy/Immunology nurse at Cleveland Clinic Children's main campus Allergy Clinic, where similar food challenges are routinely conducted. The physician investigator available will be trained in recognition and treatment of IgE mediated food reactions, will be available for immediate evaluation of any signs or symptoms of reaction.

Table 3: Oral food challenge to peanut for enrollment (Study Visit 1)

Time	Dose	Clinician Intervention *
0	5mg	Obtain weight, temperature, heart rate, blood pressure, respiratory rate, and oxygen saturation level. Peak flow will be done on patients 4+ or deemed developmentally appropriate. Full physical examination of ears, oropharynx and nose, lungs, and skin prior to administration of dose
+15 minutes	10mg	Examination of skin and auscultation of lungs prior to dose
+30 minutes	25mg	Examination of skin and auscultation of lungs prior to dose
+45 minutes	50mg	Examination of skin and auscultation of lungs prior to dose
+60 minutes	100mg	Examination of skin and auscultation of lungs prior to dose
+75 minutes	500mg	Examination of skin and auscultation of lungs prior to dose
+90 minutes	1000mg	Examination of skin and auscultation of lungs prior to dose

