If a subject does not tolerate a dose increase, then the patient will be administered a dose reduced by 25%, with increase to the originally intended dose at the subsequent visit. If the patient still does not tolerate the dose, then the decision on how to proceed will be determined at the investigator's discretion. This may involve temporarily decreasing the subject's dose, making a smaller increase, or prolonging the duration of a given dose. If any subject is unable to reach the goal maintenance dose, then the investigator may decide to continue the subject on a lower maintenance dose for the duration of the study.

Table 6: Dose Escalation Schedule

Dose of Peanut Protein	Week of Protocol
6 mg	0
12 mg	2
25 mg	4
50 mg	6
75 mg	8
150 mg	10
300 mg	12

Home Dosing

All subjects will be offered the opportunity to continue once daily consumption of the maintenance dose after the end of their study participation. This ongoing maintenance therapy is optional and will not be paid for by the study. The subjects will be instructed to otherwise continue a peanut free diet.

Follow Up

The subject will also undergo a final oral food challenge at the final visit (SV10). This food challenge will be double blind and placebo controlled. A double blind placebo controlled food challenge (DBPCFC) is the gold standard for diagnosis of food allergy and is the standard utilized for most oral immunotherapy trials at exit.

Roasted peanut powder will be utilized for the challenge, with oat flour as placebo. An individual will undergo a standard challenge described below (Table 7) with either the roasted peanut or the placebo, blinded to both subject and investigators. The same individual will then undergo a second challenge with the opposite (either peanut or placebo) either later that day or by returning to clinic the following day. Each challenge will be performed by increasing doses up to a final dose of 1000 mg of peanut protein. The individual doses will be 25, 100, 200, 300, 600, and 1000 mg of peanut protein. The highest tolerated dose will be recorded. If a patient reacted to a dose lower than 25 mg of peanut powder during the initial Oral Food Challenge then they will be started at the dose lower than where the reaction occurred for the DBOFC.

A urine pregnancy test will be repeated on all females of child bearing potential before the DBOFC.

Table 7: Double blind oral food challenge to peanut or control oat (SV 10)

Time	Dose	Clinician Intervention *

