0	25 mg peanut protein	Obtain weight, temperature, heart rate, blood pressure, respiratory rate, and oxygen saturation level. Peak flow in children ages 4+ or as developmentally appropriate. Full physical examination of ears, oropharynx and nose, lungs, and skin prior to administration of dose
+15 minutes	100 mg	Examination of skin and auscultation of lungs prior to dose
+30 minutes	200 mg	Examination of skin and auscultation of lungs prior to dose
+45 minutes	300 mg	Examination of skin and auscultation of lungs prior to dose
+60 minutes	600 mg	Examination of skin and auscultation of lungs prior to dose
+75 minutes	1000 mg	Examination of skin and auscultation of lungs prior to dose Full physical examination of ears, oropharynx and nose, lungs, and skin after completion of final dose.

*Vital signs including heart rate, blood pressure, respiratory rate and oxygen saturation level to be obtained with any change in physical exam or clinical status

If objective signs of an allergic reaction occur, then the challenge will be stopped, and the subject treated based on the presenting symptoms and clinical judgment of the supervising investigator (Table 4). If no objective signs occur within 2 hours after the last dose is consumed, then the challenge will be considered negative.

Quality of Life Questionnaire

At enrollment and after completion of the study, patients or caregivers will be asked to complete previously validated, age specific food allergy quality of life questionnaires²⁷(**Supplement 1**)

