6.5 Concomitant Therapy

Data regarding the subjects' concomitant medications will be recorded at each study visit to the Pediatric Allergy Clinic or the Clinical Research Unit. For this protocol, a prescription medication is defined as a medication that can be prescribed only by a properly authorized/licensed clinician. Medications to be reported include concomitant prescription medications, over-the-counter medications such as oral antihistamines, and supplements.

The concomitant use of antihistamines could directly affect the primary endpoint. The use of antihistamines could mask or prevent some symptoms of an allergic reaction such as urticaria or pruritus. Upon enrollment, the treating physician investigator will evaluate the specific indication for antihistamine use and will make a determination regarding continued use or discontinuation. This will be documented within the electronic medical record.

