INHALED β_2 ADRENERGIC AGONISTS	Albuterol sulfate 2.5 mg/3ml unit dose or Xopenex (levalbuterol HCl) 1.25 mg/3ml unit dose	Per Nebulizer via mouth-piece or mask as tolerated.	Delivered over 5-15 minutes and continued as necessary for bronchospasm	
 Used when bronchospasm does not respond to epinephrine 	0.15 mg/kg (minimum dose 2.5 mg) every 20 minutes for 3 doses then 0.15-0.3 mg/kg (not to exceed 10 mg) every 1-4 hours as needed or 0.5 mg/kg/hour by continuous nebulization
GLUCAGON	1 to 5 mg IV over 5 minutes	Intravenous (Glucagon administered as IV push should be reconstituted with 1 ml sterile water for injection or sterile water for reconstitution)	If no response following IVP consider IV infusion, 0.05-0.1 mg/kg/h OR 1 – 5 mg/hr titrated to clinical response	
 Used if epinephrine is not effective in patients taking β-blockers (may reverse refractory bronchospasm and hypotension) Iosotonic volume expansion may also be necessary (in some cases up to 7 L) Protection of the airway is important since glucagon can cause vomiting and risk aspiration (place in lateral recumbent position to protect airway) 	20-30 μ g/kg IV x1 (maximum 1 mg)
EPINEPHRINE IV	1:100,000 solution (0.1 mg [1 ml of 1:1000] in 100 ml saline)	Intravenous	Initial rate of 30-100 ml/hr (3-15 μ g/min) per infusion pump, titrate for hemodynamic response	
 Used in patients with poor response to IM/SQ Epinephrine Used only in profoundly hypotensive patients not responding to IV volume replacement. Every minute VS and EKG monitoring should be considered 	0.1 μ g/kg/min [0.6 X body weight (in kg) = # of mg diluted to total 100 ml saline; then 1 ml/h delivers 0.1 μ g/kg/min]
VASOPRESSOR	Dopamine (400 mg in 500 ml of 5% Dextrose)	Intravenous	2-20 μ g/kg/min, titrated to maintain systolic > 90 mm Hg	
 Used if epinephrine and volume expansion fail to alleviate hypotension. Transfer to hospital ASAP 	2-20 μ g/kg/min [6 X body weight (in kg) = # of mg diluted to total 100 ml saline; then 1 ml/h delivers 1 μ g/kg/min]

Cetirizine 10 mg	Oral	2.5-10 mg
-------------------------	-------------	------------------

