8.2 Safety and Other Assessments

Screening to ensure all subjects meet the inclusion criteria and do not meet any exclusion criteria will be performed within 1 month of the initial oral food challenge visit. At Visit 1, the physician and participant will review and update the patient's Food Allergy & Anaphylaxis Emergency Care Plan. This plan will outline the recommended treatment in case of an allergic reaction occurs during their enrollment in the study. This plan is signed by a physician, and includes emergency contact information. In addition, each study visit will include obtaining a brief interim history to ensure that no potential augmenting factors, such as viral illness, are present at the time of study drug or control drug administration. Vital signs, a targeted physical exam and conmed review will be performed prior to any study drug administration for the same purposes.

Study visit evaluation:

Brief interim history

Discussion of any interim AEs

Vital signs: Temperature, Heart Rate, Respiratory Rate

Physical Exam: Targeted assessment of General Appearance, HEENT, Cardiac, Respiratory, Abdominal, and Skin

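### The five-day antihistamine hold is written for the entry challenge only, so the exit peanut session that decides the primary endpoint can be run under an antihistamine

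*Protocol*

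**What the plan says.** **Entry challenge.** Protocol 6.1.2, Oral Food Challenge: "Subjects will be instructed to hold medications with strong antihistamine properties for five days prior to the challenge". The drugs listed there include cetirizine.

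**Routine antihistamines.** Protocol 6.5 says antihistamine use could bear directly on the primary endpoint, and explains: "The use of antihistamines could mask or prevent some symptoms of an allergic reaction such as urticaria or pruritus". Its only action is at enrollment, when the investigator "will make a determination regarding continued use or discontinuation".

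**Exit challenge.** Protocol 6.1.2, Follow Up, describes two blinded sessions, roasted peanut and oat, in either order. After the first, the child has "a second challenge with the opposite (either peanut or placebo) either later that day or by returning to clinic the following day". If objective signs occur, "the challenge will be stopped, and the subject treated based on the presenting symptoms and clinical judgment of the supervising investigator". Nothing is said about what then happens to the other session, and no antihistamine hold is given.

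**Rescue drugs.** The table in Protocol 6.5.1 includes "Cetirizine 10 mg", with a lower paediatric range.

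**Scoring.** SAP 9.2.1 takes response from the tolerated-300-mg question on the case report form for the peanut session. SAP 9.2.2 takes the change in highest and in cumulative tolerated dose from the entry challenge and that same peanut session.

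**The concern.** The trial has one primary endpoint, ten children and no concurrent control. The endpoint rests on whether signs are seen during one peanut session. The protocol names a drug class that can hide such signs, and removes it before the entry challenge but not before the exit challenge.

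An antihistamine can be present at the exit peanut session in two ways:

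- **Routine use.** A child whose antihistamine is continued under 6.5 stops it for the entry challenge and, with the text followed as written, need not stop it for the exit challenge.
- **Rescue use.** A child has oat first, reacts, is given cetirizine, and then has the peanut session the same or next day.

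In both cases 300 mg could be recorded as tolerated because skin or itch signs were suppressed. That pushes the response rate up. It also makes the within-child change in tolerated dose a comparison of a drug-free challenge with one that may not be drug-free.

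**Working it through.** **1. The plan's own figure.** Exact one-sided binomial test, n = 10, null rate 0.20, design rate 0.80, alpha 0.05 (Protocol 9.2, SAP 10.1).

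- P(X ≥ 4 | 0.20) = 0.1209, too large. P(X ≥ 5 | 0.20) = 0.0328, so success needs at least 5 of 10.
- P(X ≥ 5 | 0.80) = 0.9936. The stated power above 90% is reproduced.
- The Clopper-Pearson one-sided 95% lower bound is 0.222 at 5/10 and 0.150 at 4/10. One falsely scored responder changes the conclusion only when the count goes from 4 to 5.

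**2. Which signs can be masked.** Protocol 6.5 gives urticaria and pruritus as its examples. In Table 4 the criteria of that kind are the pruritic rash and urticaria (2 of 6 major) and persistent rubbing and scratching (2 of 5 minor): 4 of 11. Masking of every affected failure is therefore an upper bound.

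**3. Rescue route.** The documents give no rates. Assume:

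- oat comes first in half the children;
- a share q of oat sessions leads to treatment;
- a share m of the affected would-be failures is masked, meaning that an antihistamine was given and the deciding signs were suppressed.

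Effective null rate = 0.2 + 0.8 × 0.5 × q × m, and type I error = P(X ≥ 5) at that rate.

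| q | m | rate | type I error |
|---|---|---|---|
| 0.03 | 0.25 | 0.203 | 0.0348 |
| 0.03 | 0.50 | 0.206 | 0.0369 |
| 0.03 | 1 | 0.212 | 0.0414 |
| 0.10 | 0.25 | 0.210 | 0.0399 |
| 0.10 | 0.50 | 0.220 | 0.0479 |
| 0.10 | 1 | 0.240 | 0.0670 |

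The tail reaches 0.05 at a rate of 0.2224. That needs q = 0.0224 / (0.4 × m): 22% at m = 0.25, 11% at m = 0.5, 5.6% at m = 1.

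At the design rate, would-be failures affected = 10 × 0.2 × 0.5 × q = 0.03 to 0.1 child. With full masking the chance of success moves from 0.9936 to between 0.9941 and 0.9951.

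**4. Routine route.** Here neither session order nor an oat reaction is needed. Let r be the share of would-be failures on an antihistamine at the exit peanut session. Effective null rate = 0.2 + 0.8 × r × m. The 5% level is reached when r × m = 0.0224 / 0.8 = 0.028. For illustration only, r = 0.10 gives:

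- m = 0.25: rate 0.22, type I error 0.0479;
- m = 0.50: rate 0.24, type I error 0.0670.

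The documents give neither r nor m.

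**5. Could the entry hold be read to cover the exit challenge?** It stands under the open entry challenge and is not repeated under Follow Up. Even if it were read across, a session the same or next day could not satisfy five days after a cetirizine dose.

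**The case against.** The strongest objection is that the rescue route needs a chain of unlikely events: oat first, a treated reaction to oat, an antihistamine as the treatment, and a peanut failure that rests only on suppressible signs. Oat allergy is an exclusion: "Patients with oat allergy, while rare, are to be excluded as this will serve as the placebo for our exit food challenge". If peanut comes first, the 300 mg question has been answered before any rescue drug is given. This stands, and by itself the rescue route has a negligible expected effect.

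Second, staff are not blind to medication. Protocol 8.2 says vital signs, an examination and "conmed review will be performed prior to any study drug administration for the same purposes", and the schedule marks a medication review at the exit challenge. An investigator could postpone on clinical judgment. This stands in part. The review would show the drug, but its stated purpose is to look for augmenting factors such as viral illness, and no text attaches an action to it. By contrast, the protocol does write rescheduling rules for illness before the entry challenge and before initial dose escalation.

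Third, the bias is not all one way. A child who does not go on to the second session may be scored as a non-responder, since SAP 9.2.1 counts non-completion for any reason as no response. This is fair for the rescue route, but it offsets nothing in the routine route.

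Fourth, an affected case could be traced afterwards from the adverse event tables, the medication summary and the patient-level challenge listing (SAP Table 2.2). This is also true, but tracing a case does not prevent it.

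A reader might infer that the protocol tells staff to proceed with peanut after rescue treatment. It does not: it fixes the timing and is silent on this case.

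**Conclusion.** The point holds and is minor. The plan controls antihistamines at entry and leaves them to discretion at exit, where the endpoint is decided. Any effect of an antihistamine at the peanut session favours response and weakens the entry-to-exit comparison of tolerated dose.

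The rescue route alone moves the type I error from 0.033 to 0.035-0.048 with 25-50% masking. It passes 0.05 in the assumed range only near full masking with the higher reaction rates. The routine route is the more practical reason to act, but its size is unknown, and the figures in step 4 show sensitivity rather than an estimate. All results rest on assumed session order, reaction, use and masking rates.

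A reader might infer that the 5% level is breached or that the trial's conclusion is in doubt. The documents do not support that: they give no rate of use or of oat reactions, most Table 4 criteria are not of the urticaria or itch kind, and the investigator may already stop routine antihistamines.

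**What to change.** In Protocol 6.1.2, Follow Up:

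1. Apply the entry challenge's five-day antihistamine hold to both exit sessions.
2. If the first session required treatment, postpone the second until the reaction has resolved and the hold is met.
3. State an exception to the ±7 day visit window for this case, and leave any dosing during the wait to the investigator.

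The exception has to be in the protocol. SAP 6.3 sets no limit on visit timing, but that is an analysis rule prompted by pandemic scheduling and does not widen a visit window. The primary analysis stays as it is, and no sensitivity analysis is needed.

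**Cost.** A few sentences. Because staff are blinded, postponement applies to every child treated in the first session. If 20-60% of about 5 peanut-first children are treated (assumed), 5 × 0.2 to 5 × 0.6 = 1 to 3 children return later for an oat session, against 5 × 0.03 to 5 × 0.10 = 0.15 to 0.5 oat-first children for whom the delay protects the endpoint. A five-day wait fits the window only if the first session falls on or before day +2, which is 10 of the 15 possible days, so some visits will run over. Return for the second session should be followed up actively, because SAP 9.2.1 can be read to score a child who never completes it as a non-responder.
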